Follow-up data will be collected for the lifestyle interventions at 3, 6, 12, and 18 months post-randomization, with a set of 9 BP readings taken over three clinic visits at both 12 and 18 months. Termination data will be collected at three visits (7-30 days apart) at the end of the study period unless this falls within three months of the 18-month visit. For the supplements interventions, follow-up data will be collected at 3 and 6 months post-randomization during each of the two testing sequences. Termination data will be collected at 3

visits (7-30 days apart) at the conclusion of each sequence, beginning approximately two weeks before the 6-month visit for that sequence. The trial-wide data to be collected are described briefly below.

1. Random Zero Blood Pressure (BP) Measurements

Three BP measurements will be taken at each visit except SRV and FO8. Both baseline and termination BP values will be based on nine readings taken over the course of 3 visits.

2. Pulse Rate

As part of the BP protocol, 30-second pulse rate will be recorded. This variable is also of interest as a predictor of subsequent development of hypertension.

3. Body Height and Weight Measurements

Height and weight will be measured at the first screening visit so that body mass index can be calculated. Thereafter, weight only will be measured at SV3 and each follow-up visit except 1) FO8 which is the randomization visit for Stage 2 of Supplements, and 2) at F20 and F21. Baseline weight will be recorded at the third screening visit (SV3), and termination weight at the first termination visit (TV1).

4. Medical History

Medical history data (including information on smoking, drug and alcohol use, etc.) will be used to determine eligibility during screening, and thereafter to monitor for adverse effects and to assess the possible confounding effects of changes in variables such as smoking habits and medication use.

5. Physical Activity Questionnaire

Physical activity may also influence BP or response to intervention, and changes in this variable will also be assessed. The Physical Activity

Questionnaire contains information on both work and leisure physical activity.

6. General Well Being Scale, Lazarus' Hassles Scale, Multidimensional Health Locus of Control Scale, and Treatment Evaluation Scale

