systolic BP. The main endpoint of interest is change in BP from baseline to termination, with the mean at each of these two points being determined from nine BP readings (taken over three visits). There will also be the opportunity to examine BP measurements taken throughout the follow-up period. Therefore, it will be crucial to establish methodology to ensure obtaining accurate and complete BP measurements on every subject for the duration of the trial. Procedures for obtaining final BP measurements for participants who terminate early from the trial are discussed later in this chapter.

The chief concern in studies having BP as an endpoint is the amount of variability inherent in obtaining BP levels, partly due to actual variation in an individual's BP, and partly due to errors and biases in its measurement. With respect to the former, BP varies constantly due to factors such as position, emotional state, recent physical activity, room temperature, and recent consumption of certain drugs. Sources of measurement error include observer bias due to knowledge of a subject's treatment status, incorrect cuff size, non-standardized measurement practices, and digit preference.

To enhance the overall reproducibility of BP measurements in TOHP, standardized procedures for both training observers and taking measurements will be employed. Standardization of procedures for BP measurement include a uniform protocol for preparing the subjects, positioning of the participant, selection of an appropriate cuff, and imposing restrictions on smoking for a specified time period prior to BP measurement; use of a random-zero sphygmomanometer to minimize observer biases; maintaining observer blindness concerning the subject's treatment allocation; and careful maintenance of all equipment. These procedures are discussed in detail in Chapters 8, 18 and 19 of the TOHP Manual of Operations. Training of observers will include a review of written and audiovisual materials on BP measurement and Korotkoff sounds, as well as practice sessions with double stethoscopes. After completion of training, which will also include becoming familiar with the TOHP protocol, each observer will be certified, and this certification will be renewed at six-month intervals to ensure that appropriate procedures are being followed.

1. Diastolic Blood Pressure

DBP is defined as the disappearance or first absence of the fifth Korotkoff sound, not as the last sound heard.

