2. Systolic Blood Pressure

SBP is defined as the appearance of the first Korotkoff sound.

3. Ascertainment of Final BP Measurements for Participants Who Terminate Early From the Trial

It will be crucial to obtain final BP measurements from those participants who terminate early from the trial. Of particular relevance in this regard will be subjects who become frankly hypertensive during the course of the trial and for whom antihypertensive medications may be recommended. Other subjects may move away from the study area and a few may simply refuse to continue their participation in the trial.

a. Development of Hypertension or Other Conditions for which Hypotensive Drugs May Be Prescribed

Some subjects may be told by a non-study physician that their BP is high and pharmacologic therapy may be recommended or, alternatively, BP readings by study staff may on occasion be in the hypertensive range. In order to obtain termination BPs on all participants prior to the initiation of BP medications or medications for other conditions which may lower BP, the following procedures have been developed.

In an attempt to prevent study participants from being put on antihypertensive medications by non-study physicians before a set of termination BPs are obtained, both participants and their identified personal physicians will be informed of the desirability of having a set of termination BP readings prior to initiating antihypertensive medications. Upon notification of the study staff of an elevated BP reading either by the participant or the treating physician, three very brief visits will be scheduled, at 10-day intervals if possible, to determine the true mean or "underlying" BP which will be promptly reported to the subject and the treating doctor. If the physician decides to treat with antihypertensive medications after knowing the underlying BP, the participant will be terminated from the study, and this set of readings will constitute the terminating BP. If the

physician decides that treatment is not needed, the participant will be continued in the study and this procedure can be repeated if the question of a need for drug treatment arises again.

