to exclude any individuals who are at particular risk, such as those with preexisting conditions that might make participation difficult or contraindicated. Specifically, those with a history of heart disease, cancer, renal disease, diabetes, chronic gastrointestinal problems, physical handicaps that would affect participation in an exercise program, high cholesterol, and elevated serum potassium or calcium will not be permitted to enroll in TOHP. Nonetheless, there are certain parameters that will be monitored throughout the study period.

The chief safety consideration relates to individuals who may become hypertensive during the follow-up period of the trial. Clinic personnel will be instructed to implement the following procedures whenever a set of BP readings falls in the hypertensive range. A BP level that would raise the possibility of termination is a true DBP of 95 mm Hg or greater as determined by the mean of nine separate readings. Thus, if a subject's mean DBP at any single monitoring visit is greater than or equal to 93.5 (the sum of three readings greater than or equal to 281 mm Hg), that individual will be asked to return for a second visit at least one week later, at which time three additional readings will be taken. If the mean of these six readings over two visits is less than 93.5 mm Hg, the participant will be continued in the study. If, on the other hand, the mean of the six readings is 93.5 mm Hg or greater (the sum of six readings greater than or equal to 561), then the subject will be asked to return in a minimum of one week for a third set of BP measurements. At that time, if the mean DBP over nine readings is greater than or equal to 95 mm Hg (the sum of nine readings greater than or equal to 855 mm Hg), then that participant will be terminated from the study. Note that if the second or third set of three readings comprising this set of nine safety monitor readings averages 93.5 or greater, the cycle is not started again. In other words, one set of three readings triggers the collection of the set of nine safety monitoring readings, and it is the result (sum or average) of that set of nine BPs that is the basis for any future action.

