with the variance components defined as previously. These data suggest true four-year and one-year correlations of 0.85 and 0.91, respectively. Interpolating to 6 and 18 months, the true correlations in TOHP are estimated to be 0.92 and 0.90, respectively. Given three visits with three measurements each, we would expect to observe correlations of approximately 0.84 (6 months) and 0.83 (18 months). These figures lead to estimated variances for the change in means of 38.03 (standard error = 6.17) for 6 months and 40.41 (standard error = 6.36) for 18 months of observation.

Allocation of Subjects

Clinic-specific allocations are presented in Table 1.

Power_Calculations

Power calculations assume a two-sided test with significance level 0.05 and use the following formula:

Power =
$$1 - \Phi \left[z_{1-\alpha/2} - \frac{d}{\frac{\sigma^2}{n_1} + \frac{\sigma^2}{n_0}}\right]$$

where: $\Phi[\]$ = the area to the right of [] on the standard normal curve

 $z_{1-\alpha/2} = 1.96$

d = the difference in BP change between the intervention and comparison groups

 σ^2 = 6.172 for supplements and 6.362 for lifestyles

 n_1 = the number in the active intervention group

 n_0 = the number in the control group

The estimated powers associated with the expected numbers in the proposed study design are given in Table 12. All tests will have at least .90 power to detect a 2 mm Hg change in DBP.

POWER CALCULATIONS: SBP

Estimate of Variance

The same methods used for DBP have been used to estimate the components of variance for SBP. The variance of the mean BP (\vec{x}) at either baseline or termination can again be written as:

$$V_{(\vec{x})} = \sigma^2 = \sigma^2_p + \sigma^2_A/N + \sigma^2_e/NK$$

where: σ^2_{p} = between-person variance

 σ^2 A = between-visit variance

 σ^2 = within-visit variance

N = number of visits = 3

K = number of measurements per visit = 3

The variance of the difference between the baseline and termination values is a function of σ (defined above) and the tracking correlation (the variation in BP over time):

$$V(\overline{x}_1 - \overline{x}_2) = 2\sigma^2(1-\rho)$$

where:

- mean SBP at baseline

- mean SBP at termination

- the observed tracking correlation of the BP means over an average of 18 months of follow-up for the lifestyle interventions and six months of follow-up for the supplement interventions

Estimating the components of the variance of the mean BP at either base-1. line or termination

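### Two sections give opposite study status to an untreated participant averaging DBP 95 or more, and following the safety rule gives up a primary reading that could still be taken

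*Protocol*

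**What the plan says.** **Ascertainment of Endpoints, item 3a.** The introduction covers high BP found by outside physicians and also notes that "BP readings by study staff may on occasion be in the hypertensive range". Three brief visits give nine readings, and status then turns on the physician's decision. If drugs are started, the participant is terminated and those readings are the terminating BP. If the "physician decides that treatment is not needed, the participant will be continued in the study". The same steps may be gone through again at a later date. No DBP ceiling is given.

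**Safety Monitoring.** Its procedures apply "whenever a set of BP readings falls in the hypertensive range". A visit sum of 281 or more leads to a second visit, a six-reading sum of 561 or more to a third. At a nine-reading sum of 855 or more (mean 95), "then that participant will be terminated from the study". Treatment is not a condition. The lead-in is softer, saying only that such a level makes termination possible.

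**Outcome and follow-up.** The primary outcome is change in nine-reading DBP from baseline to 18 months (lifestyle) or 6 months (supplements). The Follow-Up Schedule plans lifestyle data collection "with a set of 9 BP readings taken over three clinic visits at both 12 and 18 months". Ascertainment of Blood Pressure wants methods to "ensure obtaining accurate and complete BP measurements on every subject for the duration of the trial".

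**Data Analyses.** This section warns that leaving out people withdrawn for raised BP biases the estimate. It plans nine readings over three termination visits after an early stop, plus censored-data methods.

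**The concern.** Take a participant whose nine readings average 95 or more and whose physician does not start drugs. Item 3a continues this person and Safety Monitoring terminates the same person. Neither section refers to the other, so clinics could act differently on identical readings.

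The choice affects the primary outcome. Termination removes the scheduled reading from people chosen because their DBP was high. When an intervention works, it removes more controls than treated participants. An earlier value then has to stand in. If that value is the set of readings that triggered termination, it is high partly by selection. The protocol does not say whether the safety readings may serve as the terminating set. The hypertension endpoint is not at stake, because a nine-reading mean of 95 already counts as an event.

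**Working it through.** **1. Reproducing the protocol's figures**
- Threshold: 9 × 95 = 855, as stated.
- Variance of a nine-reading mean: 109.11 + 26.76/3 + 7.42/9 = 118.85, as stated.
- Variance of 18-month change: 2 × 118.85 × (1 − 0.83) = 40.41, SD 6.36, as stated.
- SE of a lifestyle comparison, 6.36 × √(1/n₁ + 1/n₀) with Table 12 sizes: 0.47 (sodium, 327 and 416), 0.55 (weight, 308 and 232), 0.54 (stress, 242 and 319).

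**2. Simulation inputs**
- From the protocol: the variance components; visit-mean error variance 26.76 + 7.42/3 = 29.23; entry limits 75–97, 77–94 and 80–89 on cumulative means; the 281/561/855 cascade.
- Tracking: "Interpolating to 6 and 18 months, the true correlations in TOHP are estimated to be 0.92 and 0.90, respectively". The line 0.93 − 0.02 × years gives these values, and also the protocol's 0.91 at one year and 0.85 at four.
- Assumed: source-population mean 76, 80 or 84; true effect 2.0; no drift; no drug use. The cascade runs at 3, 6 and 12 months (lifestyle) or 3 months (supplements).

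**3. Who loses the scheduled lifestyle reading (source mean 76 / 80 / 84)**
- Controls terminated before 18 months: 5.68 / 7.63 / 9.85%. Of the 589 controls in Table 1, that is 0.0568 × 589 ≈ 33 to 0.0985 × 589 ≈ 58.
- Active arm terminated: 2.73 / 3.82 / 5.11%.
- Terminated controls average 97.7 / 97.8 / 97.9 on the safety set. If followed untreated, they would average 90.6 / 91.0 / 91.5 at 18 months, and 74 to 79% would then be below 95.
- A second simulation, with source mean 75 to 85 and drift of 0 or 2 mm Hg, gives about 5 to 13% of controls and 3 to 7% of the active arm.

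**4. Estimated effect when the truth is 2.0 (lifestyle)**
- Everyone followed: 2.00.
- Safety set used as the final value: 2.19 / 2.23 / 2.26. At source mean 80 the control mean rises by 0.0763 × (97.8 − 91.0) ≈ 0.52. The estimate of 2.23 implies a rise of about 0.29 in the active arm, and 0.52 − 0.29 = 0.23. The excess of 0.19 to 0.26 is 0.34 to 0.56 SE.
- Fresh nine readings, with underlying BP unchanged since the safety set (correlation 1): 2.09 / 2.10 / 2.12, at most 0.12/0.47 = 0.26 SE.
- Fresh nine readings, with the line in step 2 also applied over a few weeks (correlation about 0.93): about 2.00 to 2.02. Terminated controls then average 90.9 to 91.6 on the fresh set, close to their 18-month level.
- True effect 0: every estimate is 0.00.

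The protocol gives no correlation over a few weeks, so the range for the planned fresh set is about 2.00 to 2.12.

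**5. Supplements**
Terminated: 2.2 to 3.9% of controls and 1.0 to 1.9% of active. The fresh set with correlation 1 gives 2.03 to 2.05 and the safety set 2.07 to 2.10, against an SE of 0.57 to 0.62.

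**6. What following the untreated would gain (lifestyle)**
Scheduled readings for the untreated and a correlation-1 fresh set for the treated give 2.02–2.03, 2.04–2.06 or 2.07–2.09 when 25, 50 or 75% are treated in both arms. If 75% of controls but 50% of active participants are treated, the result is 2.09–2.13, no better than a fresh set for everyone.

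**The case against.** The sections can be read together. Item 3a is about securing readings before drugs begin, and its working trigger is a report from the participant or treating physician. Safety Monitoring is the numeric rule for study readings: below 810 continue; between 810 and 855 inform the physician and try to keep the participant in; 855 or more terminate. The untreated case in item 3a fits the middle band, which makes 95 a ceiling. This reading is possible, but item 3a names study-staff readings and sets no limit, and no text makes Safety Monitoring its ceiling. Even on this reading the scheduled primary reading is given up.

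Ending participation at 95 may also be a deliberate safety choice. Safety calls for referral and, where indicated, treatment. It does not call for an end to BP measurement.

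The most forceful objection is that the outcome is already provided for. Data Analyses rejects exclusion, plans a fresh set and adds censored-data methods. The lifestyle randomization text also asks for every effort at complete follow-up. This largely stands. A reader might infer that the plan materially inflates the primary effect, but the documents do not support that: the fresh-set bias reaches 2.12 only if underlying BP is perfectly correlated over the intervening weeks, and it nearly vanishes at 0.93. A reader might also infer that these people are dropped, which would give 1.78 to 1.85, but the protocol warns against exactly that. The different names for the two sets favour a fresh set over the safety set, though this is not stated.

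**Conclusion.** The conflict in study status is real and rests on the text alone. For an untreated participant averaging 95 or more, one section says continue, the other says terminate, and nothing says which governs. Following Safety Monitoring gives up the scheduled primary reading for up to about 6–10% of lifestyle controls and 3–5% of an active arm. That is an upper bound as regards drug use and depends on the assumed source mean, effect and absence of drift.

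The consequence for the estimate is small. A true 2.0 becomes about 2.00 to 2.12 with the planned fresh set, so bias may be negligible, and about 2.2 to 2.3 only if the safety readings were substituted. None of these figures applies the planned censored-data methods. No false difference arises when there is no effect, so an inflated false-positive rate should not be inferred. Severity is minor, and the supplements are affected less than the lifestyle arms.

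**What to change.** - State one status rule for a nine-reading mean of 95 or more, and cross-refer item 3a and Safety Monitoring.
- Let that result trigger referral and any clinical stopping of the intervention, but keep inviting the participant to the BP visits already scheduled, and record drug use.
- Use the scheduled nine readings as the primary value when the participant is untreated.
- State that the early value is the fresh termination set of Data Analyses and not the safety set, taken only where this does not delay indicated treatment.
- Keep the planned censored-data methods for treated participants.

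The cost is a few sentences and visits already on the schedule for a few percent of participants, some of whom will have left the program. The primary value would then depend on treatment status, so the treated share should be reported by arm. The gain in accuracy is small and disappears if controls are treated more often than active participants.

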If the sum of these nine readings is less than 810, the subject will continue in the study as usual. If the sum is less than 855 but greater than 810 mm Hg (90-94 mm Hg), and the sum of at least two of the three sets of three readings is less than 285 but greater than 270 mm Hg (90-94 mm Hg), then specific procedures need to be followed to inform the subject and, with permission. his/her personal physician, of the participant's actual BP readings. The principal investigator or other study physician should call or write to the

participant's physician and explain that this notification does not constitute a referral for treatment, since the literature suggests that treatment in this range is optional, but that we are notifying him/her out of an obligation to keep the physician informed about his/her patient. If possible, the principal investigator should negotiate an agreement with the participant's physician to have the participant stay in the trial on his/her assigned intervention and to have the BP readings for each subsequent visit reported to the personal physician. The participant should be contacted prior to each follow-up visit to determine if s/he has been placed on antihypertensive medication. If so, a missed visit form should be completed. If, at a subsequent visit, the subject has been off medication for at least two months, then full involvement in the study should be encouraged.

For those individuals who go on and off antihypertensive medication during the study, the final decision as to which data to use in analyses will be made at the termination of the trial. Unless contraindicated, participants should be encouraged to remain on their assigned intervention. Specific contraindications would include potassium supplementation for individuals placed on potassium-sparing diuretics, and calcium supplementation for patients placed on thiazide diuretics.

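### The 285 mm Hg visit ceiling in the notification rule makes visits averaging 95 or more count against notifying a participant whose nine-reading DBP is in the 90-94 band

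*Protocol*

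**What the plan says.** All of this is in the Protocol's Safety Monitoring chapter.

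- **Triggers.** A second visit follows when the first gives "the sum of three readings greater than or equal to 281 mm Hg". A third follows when the two visits together give "the sum of six readings greater than or equal to 561".
- **Governing principle.** Once the nine readings are taken, "it is the result (sum or average) of that set of nine BPs that is the basis for any future action".
- **Termination.** The participant leaves the study at "the sum of nine readings greater than or equal to 855 mm Hg".
- **Continuation.** "If the sum of these nine readings is less than 810, the subject will continue in the study as usual".
- **Notification.** Two conditions are joined by 'and'. The first is the nine-reading band: "If the sum is less than 855 but greater than 810 mm Hg (90-94 mm Hg". The second is a visit-level test: "the sum of at least two of the three sets of three readings is less than 285 but greater than 270 mm Hg".
- **Nature of the notice.** The participant, and with permission the personal physician, is told the readings. The physician is also told that "this notification does not constitute a referral for treatment".

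**The concern.** The band 270-285 for one visit is the band 810-855 for nine readings divided by three. As a band for the overall result it makes sense, because anything higher goes to termination. At visit level no higher branch exists, so the upper limit simply disqualifies the highest visits. A participant can sit just below the termination level, with two visits averaging above 95, and not be notified, while a participant with a lower mean is.

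This conflicts with the chapter's statement that the nine-reading result governs. It also leaves a hole. Someone with a total of 811-854 who fails the visit test is not told to continue as usual (that needs a sum below 810), is not terminated (855 or more) and is not notified.

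At stake is notice to participants and physicians on what the chapter calls its main safety consideration, the development of hypertension during follow-up. The treatment comparison is not at issue.

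**Working it through.** **1. The cut-points.** 810/9 = 270/3 = 90 and 855/9 = 285/3 = 95. The triggers are 281/3 = 93.7 and 561/6 = 93.5, consistent with the stated 93.5 for whole-number sums. The arithmetic in the chapter is sound; the fault is in how the limits are combined.

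**2. Worked examples.** All meet both triggers and have totals inside 811-854.

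| Visit sums | Total | Mean | Visits in 271-284 | Result |
|---|---|---|---|---|
| 286, 286, 280 | 852 | 94.7 | 1 | no stated action |
| 290, 286, 270 | 846 | 94.0 | 0 | no stated action |
| 288, 280, 272 | 840 | 93.3 | 2 | notified |
| 282, 280, 271 | 833 | 92.6 | 3 | notified |

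One visit of 285 or more does not by itself block notification (third row). Two always do, because only one visit is then left.

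**3. Why the triggers make this common.** Write s1 and s2 for the first two visit sums. The triggers require s1 ≥ 281 and s1 + s2 ≥ 561. If s1 is below 285, then s1 ≤ 284 and s2 ≥ 561 − 284 = 277. If s2 is also below 285, both lie in 271-284 and notification follows. So every un-notified pattern in the band has s1 ≥ 285 or s2 ≥ 285. Enumerating whole-number sums (first visit 281-330, the others 225-330) confirms it: 103,360 patterns fall in the band, 98,926 fail the visit test, and none of those has all visits below 285. These are pattern counts, not probabilities.

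**4. How often.** Inputs from Power Calculations: DBP are between-person variance 109.11, between-visit 26.76, within-visit 7.42, and true tracking correlations 0.90 (18 months) and 0.92 (6 months). The entry windows are those under Eligibility Criteria. The screening-population mean is not given, so 76, 80 and 84 were assumed. Errors were taken as normal and readings rounded to whole numbers, with 6 million people screened per setting.

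| Quantity | Result |
|---|---|
| Band un-notified, rule as written | 72-73% |
| Same, totals 846-854 only | about 60% |
| Band with two or more visits at 95 or above | 23-24% |
| Band un-notified, ceiling removed and floor kept | 9-10% |
| Band un-notified, floor removed and ceiling kept | 23-24% |
| Un-notified as a share of all participants, per monitoring visit | 1.5-2.2% |

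By subtraction, about 63% of the band (72.5 − 9.5) miss notice who would receive it if only the ceiling went.

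**5. Sensitivity.** With a screening mean of 80 and correlation 0.90, between-visit variances of 20, 15, 10 and 5 give 66%, 59%, 49% and 35% un-notified. Fixing the true DBP at values from 86 to 94 instead of modelling entry gives 69-79%.

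**6. Exactly 810.** The continue rule needs less than 810 and the notification rule more than 810, so 810 itself has no branch. It arises in about 0.2-0.3% of those reaching nine readings.

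**The case against.** Four points can be made for the rule.

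- **The principle is narrower than it looks.** The sentence about the nine-reading result restates that a high second or third set does not restart the cycle. On that reading, the visit test is an added consistency condition on the same nine readings. This softens the contradiction, but the sentence does name the sum or average as the basis for any action, and the visit test overrides it.
- **A persistence test is defensible, and the floor contributes too.** Of the un-notified, 81-83% had a third visit averaging 90 or below, and 92-93% had at least one such visit. Removing only the floor would also cut the un-notified share, to 23-24%. This stands: the 72-73% is the joint effect of both limits. It supports a floor of 270. It gives no reason for a ceiling of 285.
- **The inversion is possible, not typical.** The un-notified average 92.8-92.9 over nine readings, against 93.5-93.6 for the notified. Patterns such as 286, 286, 280, with two visits at 95 or above and none at 90 or below, are about 5% of the band. This stands, and the 72-73% should not be read as mostly higher-risk people being missed.
- **The consequence is limited.** The notice is not a treatment referral, anyone at 95 or above over nine readings is terminated, and a later visit can start a new cycle. This stands, and it limits the severity.

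**Conclusion.** The concern holds. Followed exactly, the rule withholds a safety notice because visit readings are higher, and it gives no instruction for those it leaves out. This follows from the text and needs no modelling.

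The size does depend on a model. The estimate of 72-73% of the band un-notified in a given cycle rests on the Protocol's variance components, normal errors and an assumed screening mean of 76-84. It is most sensitive to between-visit variance, and it describes a small group at any one monitoring visit. This should be corrected, but it does not threaten the trial's comparison of interventions.

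**What to change.** In the notification sentence of Safety Monitoring, let the nine-reading sum alone decide: below 810 continue as usual, 810 to 854 inclusive notify, 855 or more terminate. That agrees with the chapter's own principle, leaves no total without an action and settles the case of exactly 810.

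If a persistence test is wanted, keep only its lower limit, so that at least two of the three visit sums must exceed 270. In the same simulation 9-10% of the band would still fail it, so the text should state what happens to them and to a sum of exactly 810.

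The cost is one amended sentence, any matching text in the Manual of Operations, and a few more letters or calls.
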